#### 1.4 Endpoints

#### 1.4.1 **Primary Endpoint**

The primary endpoint is the rate of MRI-related adverse events. This endpoint was selected as the primary goal of the study is to support safety of Infinity DBS systems with MR Conditional labeling when undergoing an MRI procedure according to the approved guidelines defined in the MRI Procedure Information Clinician's Manual.

# 1.4.2 Secondary Endpoints

The following secondary endpoints are for subjects undergoing an MRI procedure with the full system configuration.

- Rate of successful MRI mode 'turn on/off' functionality of the MRI mode
- Rate of successful 'turn on/off' functionality for the stimulation
- Rate of successful adjustments to the stimulation amplitude
- Rate of successful interrogation and download of the IPG parameters
- Rate of successful ability to obtain lead impedance measurements

#### 1.4.3 Additional Safety Endpoint

• Characterization of all MRI-related adverse events.

#### 1.5 **Randomization**

This is an open label observational study, so no randomization is needed.

# 1.6 Blinding

This is an open label observational study, so no blinding is needed.

# 2.2 Statistical Methods

# 2.2.1 Descriptive Statistics for Continuous Variables

For continuous variables, results will be summarized with the numbers of observations, means, and standard deviations, and where specified in the table mockups, with median, quartiles, minimums, maximums, and 95% confidence intervals for the means.

#### 2.2.2 **Descriptive Statistics for Categorical Variables**

For categorical variables, results will be summarized with subject counts and percentages/rates, and where specified in the table mockups, with exact 95% Clopper-Pearson confidence intervals.

# 2.3 Endpoint Analysis

# 2.3.1 Primary Endpoint

The primary endpoint is the event rate of MRI-related adverse events through post-MRI procedure.

Any adverse event will be included in the primary endpoint analysis if it:

- Is classified as being MRI-related (as determined by the CEC), occurs during or after the MRI procedure, and cannot be attributed to any other cause; **and**
- Is classified as being related to the device (implanted or external component) (as determined by the Investigator); **and**
- Meets the criteria for serious adverse event **or** is a non-serious adverse event that is the result of irrecoverable failure of therapy delivery or device communication.

The clinical acceptance criterion for the rate of MRI-related adverse events is 7%,

The primary analysis will be performed on Primary Analysis Population. The primary endpoint will be summarized as number of events, number of subjects who experienced these events and percentage. The clinical acceptance criterion is satisfied if the event rate is less than 7% in both groups (leads-only and full system).

# 2.3.2 Secondary Endpoints

The following secondary endpoints will be analyzed for subjects who undergo an MRI procedure with a full system configuration. The endpoint "Rate of successful ability to obtain lead impedance measurements" will include only those subjects who had their IPG interrogated using the Clinician Programmer. Data (success or failure) for these endpoints will be collected immediately after the MRI procedure.

- Rate of successful MRI mode 'turn on/off' functionality of the MRI mode
- Rate of successful 'turn on/off' functionality for the stimulation
- Rate of successful adjustments to the stimulation amplitude
- Rate of successful interrogation and download of the IPG parameters
- Rate of successful ability to obtain lead impedance measurements

Rates will be reported as the percentage of subjects in which the device functionality could be successfully completed.

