3.1 Clinical Investigation Procedures and Follow-up Schedule

Subjects will be screened to ensure they meet all inclusion criteria and none of the exclusion criteria, and will be considered enrolled in the study after providing written informed consent. Baseline data will be collected from the subject prior to the MRI procedure, and may be performed the same day as the MRI procedure. Device functionality will be checked immediately before and after the MRI procedure. Subjects will be followed for 1 month after the MRI procedure. Participation in the clinical study will end at the conclusion of the 1 month follow-up visit, and subjects will then be followed per standard of care.

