6.3.1 Pre-MRI/MRI Procedure Data Collection/Clinical Assessments (In clinic)

Subjects will be screened to ensure that they are eligible to undergo an MRI procedure. The following data will be collected before the MRI procedure:

- Subject eligibility for MRI procedure
- DBS lead(s) information
- Adverse events
- Protocol deviations (if applicable)
- Withdrawal (if applicable)
- Device deficiency (if applicable)
- Product out of service data (if applicable)

For subjects in the full system configuration group, the following additional data will be collected:

- DBS extension and DBS IPG information
- Success or failure of 'turn on' functionality of MRI mode
- Success or failure to 'turn on/off' functionality of the stimulation
- Success or failure to make adjustments to the stimulation amplitude
- Success or failure of device interrogation and download of IPG parameters
- Success or failure to obtain lead impedance measurements (only if the Clinician Programmer is being used to interrogate the IPG)

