6.3.2 Immediate Post-MRI Procedure (In clinic, after the MRI procedure has been performed)

The following data will be collected after the MRI procedure:

- MRI scanner manufacturer/model
- Scan region (anatomic location)
- Subject position during MRI procedure
- Static field strength
- RF coil type
- RF power
 - o B1+RMS, head SAR, and/or whole body SAR, if applicable
 - Duration of each scan
- Total active scan time
- DICOM image files (de-identified), if available
- Adverse events
- Protocol deviations (if applicable)
- Withdrawal (if applicable)
- Device deficiency (if applicable)
- Product out of service (if applicable)

For subjects in the full system configuration group, the following additional data will be collected immediately after the MRI procedure:

- Success or failure of 'turn off' functionality of MRI mode
- Success or failure to 'turn on/off' functionality of the stimulation
- Success or failure to make adjustments to the stimulation amplitude
- Success or failure of device interrogation and download of IPG parameters Success or failure to obtain lead impedance measurements (only if the Clinician Programmer is being used to interrogate the IPG)

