6.4 Follow-up Assessments

6.4.1 1 Month Post-MRI Procedure Follow-up (In clinic)

The only follow-up visit for all subjects in this study will be scheduled for 30 days \pm 14 days after the MRI procedure. The follow-up visit will be conducted in the clinic and data collection will include:

- For subjects with a full DBS system implanted (includes subjects in the full system configuration group and subjects in the leads-only group who had an IPG implanted and connected to at least one lead after the MRI procedure):
 - o Success or failure to 'turn on/off' functionality of the stimulation

Clinical Investigation Plan

- o Success or failure to make adjustments to the stimulation amplitude
- o Success or failure of device interrogation and download of IPG parameters
- Success or failure to obtain lead impedance measurements (only if the Clinician Programmer is being used to interrogate the IPG)
- Adverse events
- Protocol deviations (if applicable)
- Withdrawal (if applicable)
- Device deficiency (if applicable)
- Product out of service data (if applicable)

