6.4.4 Schedule of Events

CIP Activity	Enrollment	Baseline	MRI visit		1 Month post-MRI Follow-	Unscheduled
			Pre-MRI/ MRI Procedure	Immediate Post- MRI Procedure	up (30 days ± 14 days after MRI procedure)	
Informed Consent Process	X					
Inclusion/Exclusion Criteria Check	X					
Demographics		X				
Medical condition indicated for MRI procedure		X				
Subject eligibility for MRI procedure			X			
Medical indication for DBS		X				
DBS Lead information			X			(X)
IPG and extension information			X*			(X)
MRI procedure			X			
DICOM image files				(X)		
MRI parameters				X		
Turn "on" of MRI mode			X*			
Turn "off" of MRI mode				X*		
"On/off" of stimulation			X*	X*	X**	
Adjustments to the stimulation amplitude			Х*	X*	X**	
Interrogation and download of IPG parameters			Х*	X*	X**	
Impedance testing			(X*)	(X*)	(X**)	
Session records			(X*)	(X*)	(X**)	(X**)
Adverse Events	(X)	(X)	(X)	(X)	(X)	(X)
Protocol Deviation	(X)	(X)	(X)	(X)	(X)	(X)
Withdrawal	(X)	(X)	(X)	(X)	(X)	(X)
Product Out of Service Data	(X)	(X)	(X)	(X)	(X)	(X)
Device Deficiency Information	(X)	(X)	(X)	(X)	(X)	(X)

X* = for subjects in the full system configuration group

X** = for subjects with a full DBS system implant (includes subjects in the full system configuration group and subjects in the leads-only group who had an IPG implanted and connected to at least one lead after the MRI procedure)

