15.6 Risk to Benefit Rationale

Since no design changes exist between the MR Conditional DBS system and the predicate DBS system, except for implementation of the MRI mode, the non-MR performance of these products is already well established.

In addition, the clinical evidence demonstrates that the safety and performance of the device under investigation, when used under the conditions and for the purposes intended, as specified by the manufacturer, are in compliance with the Requirements of the AIMD Directive 90/385/EEC, including the Essential Requirements.

Any undesirable side effects, under normal conditions of use, are considered to be acceptable risks when weighted against the performance of the device and benefits to the subject.

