#### 3.5 **Descriptive Endpoints or Additional Data**

- Additional safety endpoint: The frequency of all MRI-related adverse events will be reported as the number of occurrences of each event and the percentage of subjects experiencing each event in table format.
- Data (success or failure) for these outcomes will be summarized at post MRI Procedure visit
  - Rate of successful MRI mode 'turn on/off' functionality of the MRI mode
  - Rate of successful 'turn on/off' functionality for the stimulation
  - Rate of successful adjustments to the stimulation amplitude
  - o Rate of successful interrogation and download of the IPG parameters
  - Rate of successful ability to obtain lead impedance measurements

Rates will be reported as the percentage of subjects in which the device functionality could be successfully completed.

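### The MRI-mode on/off rate is tied to data collected after the MRI, but turn-on is recorded only before it, so the plan as written yields a turn-off rate labelled on/off

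*SAP*

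**What the plan says.** The secondary endpoints (CIP 4.2 and 8.2.2; SAP 1.4.2 and 2.3.2) cover device function in full-system subjects who undergo an MRI. The first is one combined rate for turning MRI mode on and off. Both analysis sections then fix the data source for the whole list: "Data (success or failure) for these endpoints will be collected immediately after the MRI procedure".

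The collection sections separate the two halves:

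- CIP 6.3.1, before the scan: "Success or failure of 'turn on' functionality of MRI mode".
- CIP 6.3.2, after the scan: "Success or failure of 'turn off' functionality of MRI mode".
- CIP 6.4.4 gives turn-on and turn-off separate rows, each marked at a single time point.
- CIP 3.1 describes checks on both sides of the scan: "Device functionality will be checked immediately before and after the MRI procedure".

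SAP 3.5 lists the same combined rate again, with post-MRI timing: "Data (success or failure) for these outcomes will be summarized at post MRI Procedure visit". SAP 6.0 repeats that line.

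**The concern.** The endpoint's name promises two functions, but the stated data source holds only one. A programmer who follows the timing sentence would produce a turn-off rate and label it on/off. A reader of the report would then believe that turn-on had been assessed.

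This matters more here than for the other four functions. CIP 15.6 explains why the rest of the system needs little new evidence: "Since no design changes exist between the MR Conditional DBS system and the predicate DBS system, except for implementation of the MRI mode". Of the five secondary endpoints, this is the only one that addresses the changed function, and the results go to the notified body (CIP 3.0).

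A second issue follows from the denominator. The endpoint counts only subjects who were scanned. If MRI mode could not be switched on and the scan was therefore not done, that failure would leave the rate altogether.

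**Working it through.** The plan gives no target or expected value for this rate, so there is no figure to reproduce. The check sets the endpoint definition against the collection lists.

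**Step 1. What is collected, and when (full-system subjects).**

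| Function | Before MRI (CIP 6.3.1) | Immediately after MRI (CIP 6.3.2) | 1 month (CIP 6.4.1) |
|---|---|---|---|
| MRI mode on | yes | no | no |
| MRI mode off | no | yes | no |
| Stimulation on/off | yes | yes | yes |
| Amplitude adjustment | yes | yes | yes |
| Interrogation and download | yes | yes | yes |
| Impedance (Clinician Programmer only) | yes | yes | yes |

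The schedule in CIP 6.4.4 agrees.

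**Step 2. Apply the timing rule.** Keeping only the column for immediately after the MRI leaves a result for four of the five endpoints in full. For MRI mode it leaves turn-off alone. The mismatch is specific to this endpoint.

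**Step 3. Look for turn-on elsewhere in the SAP.** SAP 3.5 and 6.0 use post-MRI timing, and no later time point holds a turn-on field. SAP 2.9 sets evaluability by testing done immediately after the scan. No readable SAP text assigns the pre-MRI record to any analysis, or says how turn-on and turn-off would combine into one result per subject.

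**Step 4. Size, by illustration.** CIP 5.8 plans about 35 full-system subjects. Assume 35 attempted turn-ons, one turn-on failure and no turn-off failures. The failure count is an assumption.

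- If the failure prevents the scan, 34 subjects are scanned. The rule as written gives 34/34 = 100%. Turn-on among those attempted is 34/35 = 97.1%.
- If the failure is recorded but the subject is still scanned, the rule as written gives 35/35 = 100%. Turn-on is again 34/35 = 97.1%.

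Either way the omission is worth 1/35 = 2.9 percentage points per failure.

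**The case against.** The strongest reply is that the endpoint's name already includes both halves and both are collected, so any statistician would join the pre- and post-MRI fields. Moreover, switching MRI mode off presupposes that it was on, so a successful turn-off in a scanned subject implies that turn-on worked. Scans must also follow the Clinician's Manual (CIP 6.3), which makes a scanned subject with an unresolved turn-on failure unlikely.

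Much of this is fair. The data exist, so the gap lies in the analysis definition and not in collection. But joining the fields departs from the stated timing rule, and the text does not say whether to report a composite or two rates. The inference from turn-off to turn-on, which the documents do not state, also points to the denominator: among scanned subjects a turn-on rate is close to 100% by construction, so the informative figure is the one among subjects in whom turn-on was attempted.

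A second reply is that the restriction to scanned subjects is deliberate and consistent, and that a failure without a scan would appear elsewhere. It is consistent, so the attempted denominator should be presented as a change, with the scanned-only figure kept beside it. Such failures would be reported to the sponsor as device deficiencies (CIP 7.4.2) and might appear among the early-termination reasons (SAP 3.3). No readable SAP section summarises device deficiencies, however.

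A reader might go further and infer that SAP 3.5 names a visit that does not exist, or that it must mean the 1-month visit. The documents do not support either inference. Time points have visibly been removed elsewhere in the SAP, for example in 2.3.1, and words may be missing from this line too. The point does not depend on it.

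**Conclusion.** The mismatch is real: the stated data source gives a turn-off rate under an on/off label. Confidence is high, because it rests on the documents' own collection lists. The table mockups and case report forms are not shown, so a mockup that specifies turn-on cannot be ruled out.

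The impact is minor. The rate is descriptive, there is no hypothesis test (SAP 2.11), and success depends on the primary endpoint alone (CIP 8.9, SAP 2.7). The size of about 2.9 points per omitted failure assumes about 35 full-system subjects. Nothing in the documents says that turn-on failures will occur or that they will prevent scans.

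A reader might also infer that other secondary rates lose failures through the exclusion of incomplete testing in SAP 2.9, or through the Clinician Programmer condition on impedance. The text does not establish this. Success and failure are both recorded values, so a failed test is not missing data, and a failed interrogation has its own endpoint.

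**What to change.** In SAP 2.3.2, and in the matching MRI-mode lines of SAP 3.5 and 6.0, replace the combined rate with two descriptive rates:

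1. Turn-on success, from the pre-MRI record, among all full-system subjects in whom it was attempted, with the scanned-only figure alongside.
2. Turn-off success, from the immediate post-MRI record, among full-system subjects who were scanned.

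Correct the timing sentence in SAP 2.3.2 so that it excepts turn-on, and record the departure from CIP 8.2.2 in SAP 6.0.

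The cost is low. Both fields are already collected (CIP 6.3.1 and 6.3.2), and case report form data are collected for every enrolled subject (CIP 11.4), so the work is wording. Recording the change in the SAP avoids amending CIP 8.2.2, which would need documented IRB/EC acknowledgement or approval (CIP 10.3) at up to 25 centers. The downside is that the reported turn-on rate may be slightly lower than a scanned-only figure, and the two denominators may differ and need a footnote.

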# 2.9 Handling of Missing Data

No imputation techniques will be implemented in the analysis. The secondary endpoints will be evaluated in subjects who undergo an MRI procedure with a full system configuration. Subjects who don't have the IPG testing complete immediately after MRI procedure will be excluded from the related endpoint analysis.

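### Four device functions are tested before and after the scan but analysed from the post-MRI test alone, so old faults and new losses are pooled

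*SAP*

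**What the plan says.** Protocol 3.1 sets up a paired check: "Device functionality will be checked immediately before and after the MRI procedure". Protocol 6.3.1 lists the pre-scan items for the full system group, among them "Success or failure to 'turn on/off' functionality of the stimulation", and with it amplitude adjustment, interrogation and download of IPG parameters, and lead impedance if the Clinician Programmer is used. Protocol 6.3.2 lists the same four items after the scan, and the schedule of events (6.4.4) marks them at both times.

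The analysis uses the second test only. SAP 2.3.2, repeating protocol 8.2.2, says "Data (success or failure) for these endpoints will be collected immediately after the MRI procedure" and defines the statistic so: "Rates will be reported as the percentage of subjects in which the device functionality could be successfully completed". The summary that the SAP adds in sections 3.5 and 6.0 stays at the same time point: "Data (success or failure) for these outcomes will be summarized at post MRI Procedure visit". SAP 2.9 also sets the denominator by the post-scan test: "Subjects who don't have the IPG testing complete immediately after MRI procedure will be excluded from the related endpoint analysis".

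MRI mode, the fifth secondary endpoint, is collected differently. Before the scan the item is "Success or failure of 'turn on' functionality of MRI mode", and after it "Success or failure of 'turn off' functionality of MRI mode".

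**The concern.** The study asks whether the system remains safe and functional when an MRI is done under the approved conditions. For the four paired functions, the natural quantity is change across the scan: of the devices that worked before, how many did not work after. The planned percentage describes the state of the device after the scan, whatever its state before.

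The study is single-arm, and the SAP plans no covariate adjustment (2.12) and no sensitivity analysis (2.13). For these function rates, the subject's own pre-scan result is the only reference measured in the study. If it is left out, a reader of the final report who sees one failure cannot tell from the endpoint whether the scan preceded it or followed it.

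**Working it through.** **Which functions are paired**

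| Function | Before MRI (protocol 6.3.1) | After MRI (protocol 6.3.2) | Used in SAP 2.3.2 |
|---|---|---|---|
| Stimulation on/off | yes | yes | after only |
| Amplitude adjustment | yes | yes | after only |
| Interrogation/download | yes | yes | after only |
| Impedance (Clinician Programmer users) | yes | yes | after only |
| MRI mode | 'turn on' only | 'turn off' only | not a paired test |

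No legible section of either document tabulates the pre-MRI result, conditions on it, or compares it with the post-MRI result.

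**Denominator.** Protocol 5.8 gives about 35 subjects per configuration group, 5% attrition and up to 74 enrolled. Check: 2 × 35 = 70, and 70/(1 − 0.05) = 73.7, which rounds up to 74. The stated total reproduces, so n = 35 is a fair working figure for the full system group. The secondary endpoints have no target, alpha or power to reproduce.

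**Formulas.** Let a be the subjects with a fault before the scan that persists, and b the subjects who lose the function across the scan and still fail at the post-MRI test.
- Planned rate = (n − a − b)/n
- Newly lost rate = b/(n − a)
- Success among those working before = (n − a − b)/(n − a)

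**Results for n = 35.** The fault counts are assumptions. Intervals are exact 95% Clopper-Pearson, the method named in SAP 2.2.2.

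| a (old) | b (new) | Planned rate | Newly lost | Success among those working before |
|---|---|---|---|---|
| 1 | 0 | 34/35 = 97.1% (85.1 to 99.9) | 0/34 = 0% (0 to 10.3) | 34/34 = 100% |
| 0 | 1 | 34/35 = 97.1% (85.1 to 99.9) | 1/35 = 2.9% (0.1 to 14.9) | 34/35 = 97.1% |
| 2 | 0 | 33/35 = 94.3% (80.8 to 99.3) | 0/33 = 0% (0 to 10.6) | 33/33 = 100% |
| 1 | 1 | 33/35 = 94.3% (80.8 to 99.3) | 1/34 = 2.9% (0.1 to 15.3) | 33/34 = 97.1% |
| 0 | 2 | 33/35 = 94.3% (80.8 to 99.3) | 2/35 = 5.7% (0.7 to 19.2) | 33/35 = 94.3% |

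The planned rate depends only on a + b, so it cannot separate the rows that share a total. Each subject moves it by 1/35 = 2.9 points. The impedance denominator is not given; at an assumed 20 it would be 1/20 = 5 points per subject.

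**Direction.** Post-MRI failures number a + b, which is never less than b. Among subjects tested after the scan, a persisting old fault can therefore only add to the failures.

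**Why two separate percentages would not be enough.** Suppose one subject fails before and recovers, while another works before and fails after. The success rate is then 34/35 at both times, yet the newly lost rate is 1/34 = 2.9%. Only the cross-table shows the change.

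**The case against.** The case for leaving the plan alone has real force.

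- **Losses do have routes into the report.** A reader might infer that newly lost function is never reported. The documents do not support that. Every new loss still failing at the post-MRI test is a failure in the planned rate. Irrecoverable loss of therapy or communication can enter the primary endpoint if it is an adverse event that is MRI-related and device-related (SAP 2.3.1). Adverse events are summarised by relationship (SAP 3.2), and MRI-related ones are tabulated (SAP 3.5). Malfunctions go on a CRF (protocol 7.4.2), although no legible SAP section tabulates them. What remains uncovered is narrower: a recoverable loss, or one that is not an adverse event, has no planned pre/post tabulation.
- **The plan does not attribute these failures to MRI.** A reader might infer that an old fault is held against the scan. The rates are descriptive, with no threshold and no hypothesis test (SAP 2.11). Attribution is made for adverse events, where the CEC weighs other causes and pre-existing condition (protocol 7.3). The risk lies in how the percentage is read.
- **Faulty devices may not reach the scanner.** Subjects are screened for MRI eligibility beforehand (protocol 6.3.1), which may remove some. The Clinician's Manual criteria are not in the documents, so the number is unknown. A pre-scan success-or-failure field allows for failures but does not show that they occur.
- **Not everything is visible.** The SAP refers display detail to table mockups that are not provided, and parts of its text are blacked out. A pre-MRI column could exist there.

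All four points stand, and they limit the size of the concern. None of them supplies a planned rate of newly lost function.

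**Conclusion.** The point holds in a limited form. For the four paired functions, the legible plan ignores a pre-scan result that it collects, pools old faults with new losses, and provides no rate of newly lost function.

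The consequence is modest. Study success rests on the primary endpoint (protocol 8.9, SAP 2.7) and is untouched. A reader might go further and infer that the endpoint could conceal harm from the scan. The arithmetic does not support that, because the failure count among tested subjects cannot fall below the number of new losses present at that test. The weakness is that the rate is hard to interpret: at n = 35 the same 97.1% fits a newly lost rate of 0% or 2.9%, and the same 94.3% fits 0%, 2.9% or 5.7%.

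These figures assume 35 full-system subjects and one or two faults. The true frequency of pre-scan faults cannot be derived from the documents and may be zero. MRI mode falls outside the point because it has no paired test.

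**What to change.** In SAP 2.3.2, keep the all-subjects post-MRI success rate as planned. For stimulation on/off, amplitude adjustment, interrogation/download and impedance, add:

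1. a pre-by-post 2x2 table of success and failure;
2. the post-MRI success rate among subjects with pre-MRI success, with an exact 95% Clopper-Pearson interval;
3. a listing of each subject who newly lost a function.

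State that MRI mode is left out of the paired table because 'turn on' is tested only before the scan and 'turn off' only after it. Reconcile that with the sentence placing all the secondary endpoint data after the scan.

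The cost is a few lines of SAP text, one table and one listing. The data are already collected under protocol 6.3.1 and 6.3.2, so no visit, CRF or sample size change follows. If no pre-scan failures occur, the table shows that and makes the planned rate easier to interpret.
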